### 3.3. Sample Size Considerations

Sample size in the Phase 1b part of the study is based on operational consideration.

The sample size in the Phase 2 POC study is based on the primary endpoint, SRI-4 Response at Day 210. Based on efficacy data from a recently completed study with Ustekinumabiii, where the primary endpoint was also SRI-4, the sample size in the phase 2 part of the BOS161721-02 study is set at 96 evaluable patients. In the Ustekinumab study of 102 patients, a statistically significant difference in SRI-4 response was shown in favor of Ustekinumab (62% of Ustekinumab treated patients achieved SRI-4 response vs. 33% in patients receiving placebo). The Ustekinumab phase 2 study is an appropriate comparator to BOS161721-02 because both studies share the same primary endpoint of SRI-4 response and BOS161721 and Ustekinumab have overlapping mechanisms of action (T follicular helper and Th17 cell biology).

Sponsor: Boston Pharmaceuticals, Inc.  
Protocol Number: BOS161721-02  
SAP Version and Date: Version 4.0, 23Apr2021

Approximately 110 additional patients will be randomized in a 2:1 ratio to BOS161721 versus placebo to achieve approximately 96 evaluable patients in the FAS of the phase 2 portion. This assumes 14 patients will discontinue prior to having received treatment or having completed a post-baseline efficacy measure. Enrollment and randomization will be monitored in a blinded fashion and may be increased if needed to ensure at least 96 evaluable patients are randomized into the FAS (see Section 6.1).

A total of 96 evaluable patients randomized provides 80% power to detect a treatment difference of 29% in SRI-4 response rates at Day 210, based on a targeted 2-sided significance level of 10% and using a 2-sided Pearson's chi-squared test. This assumes a response rate of 62% for BOS161721 and 33% for placebo.

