**Table 2**

| Analysis   | Analysis Population | Criteria   |
|--|---------------------|--|
| Primary Analysis

LOCF for missing data,
Medication
Failures=Non-Responder | FAS                 | 
The primary analysis of the primary efficacy endpoint will be performed based on LOCF methods for missing data.
 
 
(1) Medication failures are considered non-responders on and after the date of medication failure
 
(2) Early withdrawals/discontinuations prior to study day 159 will be considered non-responders after the date of early withdrawal/discontinuation
 
 |

|  |     |  |
|--|-----|--|
|  |     | 
 
a. If patient is a medication failure prior to withdrawal/discontinuation, patient will be considered a non-responder on and after the date of medication failure.
 
b. In case of early withdrawal/discontinuation after study day 159 but before Day 210 such that patient has Day 180 data but is lacking Day 210 data in a patient without medication failure, the Day 180 data will be carried forward to Day 210.
 
 
(3) Patients with missing Day 180 and Day 210 data without prior medication failure and without early withdrawal/discontinuation prior to study day 159 are considered not evaluable and are excluded from analysis
  |

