Statistical testing data will be omitted from MAD Phase 1b treatment group displays.

A summary of disposition of SRI-4 response per the primary analysis at day 210 will be presented by study phase and treatment group in the FAS and PP. Sensitivity analysis 2 (LOCF, Exclude Medication Failures) will also be performed for disposition of SRI-4 response at day 210. These summaries will include the number of SRI-4 responders and the number of SRI-4 non-responders with a breakdown of reasons for non-response (early withdrawal, medication failure, <4-point reduction from baseline in SLEDAI-2K total score, new BILAG 1A/2B, and PGA worsening). Denominators for percentages will be the number of patients eligible for SRI-4 response analysis (patients not deemed not evaluable) defined as those with data for PGA, SLEDAI-2K and BILAG at Day 210 (whether or not due to LOCF, FAS analysis).

A listing of SRI Response data at Days 30, 60, 90, 120, 150, 180 and 210 will be presented in the FAS. A listing of SRI-4 Response at Day 210 (Primary and Sensitivity Analyses) will also be presented in the FAS. A listing of patients with medication failures, early withdrawals/discontinuations and those excluded from the primary efficacy analysis will also be provided for all randomized patients.

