### 7.2.1. Proportion of Patients with SRI-4 Response at Each Visit

The primary analysis methods described in Section 7.1.1 and Table 2 will be repeated for each nominal visit and will be presented by study phase and treatment group in the FAS. Other analyses described in Section 7.1.1 may also be performed. The 3 components will not be summarized separately by visit. In case of missing data, LOCF methods will be implemented as described in section 5.4 and Table 1. LOCF will only be implemented with the most recent prior nominal visit. If the most recent prior nominal visit is missing, occurred more than 30 days before, or is not evaluable, LOCF is not implemented. For example, if Day 30 SLEDAI assessment is complete but Day 60 and Day 90 SLEDAI assessments are missing, Day 60 will implement LOCF from Day 30 assuming Day 30 is within 30 days of Day 60 and Day 60 SLEDAI will be included in the analysis but Day 90 will not carry forward from Day 60 and thus Day 90 will be considered not evaluable and will be excluded from the analysis. Similarly, if Day 150 assessments are complete but Day 180 and Day 210 are missing, Day 180 will implement LOCF from Day 150 assuming Day 150 is within 30 days of Day 180 and will be included in the analysis but Day 210 will not carry forward from Day 180, will be considered not evaluable, and will be excluded from the analysis.

Sponsor: Boston Pharmaceuticals, Inc.  
Protocol Number: BOS161721-02  
SAP Version and Date: Version 4.0, 23Apr2021

If a patient is a medication failure, the patient is considered to be a non-responder at timepoints on or after the first date of prohibited medication/unallowable CS usage.

If a patient discontinues/withdraws early, the patient will be considered a non-responder after the date of discontinuation/withdrawal (unless the patient had a prior medication failure in which case the patient is considered a non-responder on and after the date of medication failure).

The denominators for analyses will be the number of patients in the FAS with an evaluable post-baseline SRI-4 assessment defined as those with data for PGA, SLEDAI-2K and BILAG (whether observed or imputed via LOCF depending on the analysis) at a given visit.

A graphical display of SRI-4 response by study phase, treatment group, and visit in the FAS will be presented.

Statistical testing data will be omitted from MAD Phase 1b treatment group displays.

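### The denominators for the by-visit SRI analyses and BICLA leave out patients without visit data whom the SAP has already classed as non-responders

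*SAP*

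**What the plan says.** **Non-responder rules.** For the primary Day 210 analysis, SAP 7.1.1 Table 2 states: "Early withdrawals/discontinuations prior to study day 159 will be considered non-responders after the date of early withdrawal/discontinuation". Medication failures are non-responders from the date of failure. Item 3 of the same table excludes only patients who lack both Day 180 and Day 210 data and had neither a prior medication failure nor a withdrawal before study day 159. Section 7.2.1 repeats the primary methods at each nominal visit and restates the rule: "If a patient discontinues/withdraws early, the patient will be considered a non-responder after the date of discontinuation/withdrawal".

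**Denominators.** Section 7.2.1 then sets the denominator for its analyses as FAS patients "with an evaluable post-baseline SRI-4 assessment defined as those with data for PGA, SLEDAI-2K and BILAG", observed or by LOCF, at the visit. Sections 7.2.2 (SRI-5), 7.2.3 (SRI-6) and 7.2.7 (BICLA) use the same formula.

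**Disposition summary.** The text after Table 2 in 7.1.1 describes the denominator as everyone not classed as not evaluable, and in the same sentence narrows it: "defined as those with data for PGA, SLEDAI-2K and BILAG at Day 210 (whether or not due to LOCF, FAS analysis". The summary also lists early withdrawal and medication failure among its reasons for non-response.

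**Carry-forward.** Under 5.4 and 7.2.1, LOCF uses only the most recent prior visit, and only within 30 days. Under the out-of-window rules in 7.1.1, a Day 180 assessment must fall at least 159 days after first dose to be carried to Day 210.

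**The concern.** The plan chose non-responder imputation for patients who fail or leave. That choice works only if those patients are in the denominator. A denominator built on having data for three instruments at the visit removes the ones who have left, and LOCF cannot bring them back beyond the first missed visit.

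The endpoints concerned are listed secondary endpoints, and in Phase 2 they are tested with the primary methods. If the literal rule is programmed:

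- response rates rise in both arms;
- the difference is distorted, most of all when dropout differs by arm;
- the Day 210 row of the by-visit table can contradict the primary analysis of the same endpoint at the same visit.

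Two programmers could each follow the SAP and produce different results.

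**Working it through.** **1. The plan's own figure.** Inputs from SAP 3.3: "80% power to detect a treatment difference of 29% in SRI-4 response rates at Day 210"; "This assumes a response rate of 62% for BOS161721 and 33% for placebo"; "Approximately 110 additional patients will be randomized in a 2:1 ratio to BOS161721 versus placebo"; two-sided 10% level. For allocation k = 2, with p1 = 0.33, p2 = 0.62 and pooled rate (0.33 + 2 × 0.62)/3 = 0.523:

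- n(placebo) = [1.645 × √(0.523 × 0.477 × 1.5) + 0.842 × √(0.33 × 0.67 + 0.62 × 0.38/2)]² / 0.29² = 26.6, so 27 + 54 = 81.
- The continuity correction raises this to 32 + 64 = 96, the stated number, which is also 110 − 14.
- Without the correction, power at 96 is 86.2% (85.8% by exact enumeration).

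The sample size is therefore not in question. The 14 patients allowed for are losses before treatment or before any post-baseline efficacy measure. Nothing is stated about dropout after FAS entry.

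**2. One patient through the rules.** Suppose a patient is assessed at Day 90, leaves the study on study day 100 and has no medication failure.

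| Analysis | Class under the non-responder rule | In the denominator? |
|---|---|---|
| Primary, Day 210 (Table 2 item 2) | Non-responder | Yes |
| By-visit, Day 120 (7.2.1) | Non-responder | Only if Day 90 data can be carried |
| By-visit, Days 150, 180, 210 (7.2.1) | Non-responder | No: no data, nothing to carry |
| Disposition, Day 210 (7.1.1) | Non-responder, reason early withdrawal | Yes or no, depending on which half of the sentence is followed |

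**3. Size.** Let r be the rate with dropouts counted as failures and d the proportion with no data. All responders have data, so the data-only rate is r/(1 − d). Holding r at the planning rates of 62% and 33% (29 points), with d assumed:

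| d active / d placebo | Active | Placebo | Difference |
|---|---|---|---|
| 10% / 10% | 0.62/0.90 = 68.9% | 0.33/0.90 = 36.7% | 32 points |
| 20% / 20% | 0.62/0.80 = 77.5% | 0.33/0.80 = 41.3% | 36 points |
| 25% / 10% | 0.62/0.75 = 82.7% | 0.33/0.90 = 36.7% | 46 points |
| 10% / 25% | 0.62/0.90 = 68.9% | 0.33/0.75 = 44.0% | 25 points |

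**4. Effect on a test.** These are illustrative counts on 64:32, using Pearson's chi-square without correction.

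- All counted: 33/64 vs 12/32. X² = 96 × (33×20 − 12×31)² / (64×32×45×51) = 1.69, p = 0.19.
- 13 active and 3 placebo removed: 33/51 vs 12/29. X² = 80 × (33×17 − 12×18)² / (51×29×45×35) = 4.09, p = 0.043.
- 6 active and 8 placebo removed: 33/58 vs 12/24. X² = 82 × (33×12 − 12×25)² / (58×24×45×37) = 0.33, p = 0.57.

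The same responders give a result on either side of the 0.10 threshold.

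**5. An adjacent conflict.** For withdrawal on or after study day 159 with neither Day 180 nor Day 210 data, the early-withdrawal paragraphs of 7.1.1 say non-responder at Day 210. Table 2 item 3 makes the same patient not evaluable and excludes them.

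**The case against.** A reader might infer that the primary endpoint itself becomes a completer analysis and that non-responder imputation is cancelled throughout. The SAP does not support that. The Day 210 test takes its inclusion rule from Table 2, which keeps withdrawals before study day 159 as non-responders and names the only missing-data pattern it excludes. The data-based sentence in 7.1.1 sets percentages for a descriptive disposition summary, and its own parenthesis and list of reasons point towards keeping these patients.

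Three further points on the other side are fair:

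- Section 7.2.1 opens by invoking the primary methods and restates the non-responder rule, so the intent can be inferred.
- Patients who stop treatment or become medication failures but are still assessed stay in even the literal denominator. How many early withdrawals lack later data depends on follow-up arrangements that the SAP leaves to the protocol.
- Any size depends on dropout figures that the SAP does not give. Larger distortions can be produced by choosing a more uneven split between arms, but nothing in the SAP supports a particular split.

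What remains is that 7.2.1 sets the denominator for the analyses, not only for a display, and that 7.2.2, 7.2.3 and 7.2.7 repeat it. Inferred intent does not override an explicit rule when tables are programmed.

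**Conclusion.** The SAP contradicts itself, and the by-visit SRI-4, SRI-5, SRI-6 and BICLA denominators are wrong as written. Followed literally, they drop patients who have left and have no visit data, although the plan has classed them as non-responders. The Day 210 disposition summary has the same wording and is internally inconsistent. The primary Day 210 test is not changed by these sentences. The separate conflict over withdrawal on or after study day 159 does touch its inclusion rule.

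Under 10% to 25% dropout per arm, the planned 29 points would appear as about 25 to 46 points. The difference widens when dropout is equal or heavier on active, and can narrow when placebo loses more. This rests on assumed dropout and on every such patient lacking all usable data at the visit, so it is an illustration of scale and not a forecast.

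**What to change.** Before unblinding:

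1. In 7.1.1 (disposition summary), 7.2.1, 7.2.2, 7.2.3 and 7.2.7, define the denominator as all FAS patients except those expressly not evaluable (Table 2 item 3 and its by-visit equivalent) and those excluded for missing pre-treatment SLEDAI-2K, PGA or BILAG data. State that medication failures and early withdrawals count as non-responders whether or not they have data at the visit.
2. Give Sensitivity Analysis 2 its own denominator sentence. It excludes these patients by design and is used for both the disposition summary and BICLA.
3. Choose one classification for withdrawal on or after study day 159 with no Day 180 or Day 210 data, and state it identically in the early-withdrawal paragraphs and Table 2 item 3. Without this, the new denominator would both include and exclude the same patient.
4. Check in programming that the Day 210 row of the by-visit SRI-4 table reproduces the primary counts.

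The cost is one sentence repeated in five sections, two clarifications and a programming check. Displayed response percentages will be lower than under the literal rule.

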## 7.2. Secondary Efficacy Endpoints and Analyses

PK and PD measures are the secondary endpoints for the Phase 1b MAD part of the study and exploratory endpoints for the POC part of the study. Those analyses are described in Section 8.

### 7.2.1. Proportion of Patients with SRI-4 Response at Each Visit

The primary analysis methods described in Section 7.1.1 and Table 2 will be repeated for each nominal visit and will be presented by study phase and treatment group in the FAS. Other analyses described in Section 7.1.1 may also be performed. The 3 components will not be summarized separately by visit. In case of missing data, LOCF methods will be implemented as described in section 5.4 and Table 1. LOCF will only be implemented with the most recent prior nominal visit. If the most recent prior nominal visit is missing, occurred more than 30 days before, or is not evaluable, LOCF is not implemented. For example, if Day 30 SLEDAI assessment is complete but Day 60 and Day 90 SLEDAI assessments are missing, Day 60 will implement LOCF from Day 30 assuming Day 30 is within 30 days of Day 60 and Day 60 SLEDAI will be included in the analysis but Day 90 will not carry forward from Day 60 and thus Day 90 will be considered not evaluable and will be excluded from the analysis. Similarly, if Day 150 assessments are complete but Day 180 and Day 210 are missing, Day 180 will implement LOCF from Day 150 assuming Day 150 is within 30 days of Day 180 and will be included in the analysis but Day 210 will not carry forward from Day 180, will be considered not evaluable, and will be excluded from the analysis.

Sponsor: Boston Pharmaceuticals, Inc.  
Protocol Number: BOS161721-02  
SAP Version and Date: Version 4.0, 23Apr2021

If a patient is a medication failure, the patient is considered to be a non-responder at timepoints on or after the first date of prohibited medication/unallowable CS usage.

If a patient discontinues/withdraws early, the patient will be considered a non-responder after the date of discontinuation/withdrawal (unless the patient had a prior medication failure in which case the patient is considered a non-responder on and after the date of medication failure).

The denominators for analyses will be the number of patients in the FAS with an evaluable post-baseline SRI-4 assessment defined as those with data for PGA, SLEDAI-2K and BILAG (whether observed or imputed via LOCF depending on the analysis) at a given visit.

A graphical display of SRI-4 response by study phase, treatment group, and visit in the FAS will be presented.

Statistical testing data will be omitted from MAD Phase 1b treatment group displays.

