#### **Early Treatment Withdrawals/Discontinuations:**

For early treatment withdrawal/discontinuation prior to study day 159 (180 days – 21 day treatment window), patient will be considered a non-responder after the date of early treatment withdrawal/discontinuation assuming the patient was not considered a medication failure prior to or on the date of early withdrawal/discontinuation for the primary efficacy analysis.

For early treatment withdrawal/discontinuation on or after study day 159 (180 days – 21 days) such that patient has data for nominal visit Day 180 but not for nominal visit Day 210, Day 180 data will be carried forward to Day 210 for assessment of SRI-4 response.

For early treatment withdrawal/discontinuation on or after study day 159 (180 days – 21 days) such that patient does not have data for nominal visit Day 180 and Day 210, the patient will be considered a non-responder on Day 210.

For early treatment withdrawal/discontinuation on Day 210 such that patient has data for nominal visit Day 210, the Day 210 data will be used for assessment of SRI-4 response.

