|  |     | 
(2) Early withdrawals/discontinuations prior to study day 159 will be considered not evaluable and will be excluded from analysis after the date of early withdrawal/discontinuation
 
 
a. If patient is a medication failure prior to withdrawal/discontinuation, patient will be considered not evaluable and excluded on and after the date of medication failure.
 
b. In case of early withdrawal/discontinuation after study day 159 but before Day 210 such that patient has Day 180 data but is lacking Day 210 data in a patient without medication failure, the Day 180 data will be carried forward to Day 210.
 
 
(3) Patients with missing Day 180 and Day 210 data are considered not evaluable and are excluded from the sensitivity analysis
  |
| Sensitivity Analysis 3:
Observed (no LOCF for missing data), Exclude Medication Failures                        | FAS | 
A sensitivity analysis of the primary efficacy endpoint may be performed based on purely observed data. No LOCF imputations will be performed for missing data.
 
Additional criteria are as follows:
 
 
(1) Medication failures are considered not evaluable and are excluded from the sensitivity analysis on and after the date of medication failure
 
(2) Early withdrawals/discontinuations prior to Day 210 will be considered not evaluable and are excluded from the sensitivity analysis after the date of early withdrawal/discontinuation
 
a. If patient is a medication failure prior to withdrawal/discontinuation, patient will be considered not evaluable and excluded on and after the date of medication failure.
 
 
(3) Patients with missing Day 210 data are considered not evaluable and are excluded from the sensitivity analysis
 
If lab component scores are carried forward from Day 180 to Day 210 in order to assign a Day 210 grade in the primary analysis, the Day 210 assessment will be considered not evaluable for this sensitivity analysis.
 |
| Sensitivity Analysis 4:
LOCF for missing data,
Medication Failures=Non-
Responder, Logistic
Regression | FAS | 
CCI
 
[REDACTED]
 
[REDACTED]
 
[REDACTED]
   |

Sponsor: Boston Pharmaceuticals, Inc.  
Protocol Number: BOS161721-02  
SAP Version and Date: Version 4.0, 23Apr2021

Additional sensitivity analyses may be performed to consider the effect of missing data.

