Approach 2: Corresponding to Sensitivity Analysis 2 Methods (Exclude Medication Failure): If a patient is a medication failure, all assessments on and after medication failure date will be considered not evaluable and will be excluded. In the case of patients who withdraw/discontinue early without prior medication failure, all assessments after the early withdrawal date will be considered not evaluable and will be excluded. In case of early withdrawal/discontinuation after Day 180 but before Day 210 such that patient has Day 180 data but is lacking Day 210 data in a patient without medication failure, the Day 180 data will be carried forward to Day 210.

Statistical testing data will be omitted from MAD Phase 1b treatment group displays.

PGA observed results will be presented in a data listing for all randomized patients.

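### Section 7.2.1 scores every early discontinuer as a non-responder, while the primary rule it says it repeats carries Day 180 forward to Day 210 for late stops, so the by-visit Day 210 row may differ from the primary result

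*SAP*

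**What the plan says.** All references are to SAP V4.0.

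- **Primary analysis, text.** Section 7.1.1, under Early Treatment Withdrawals/Discontinuations, takes a patient who stops on or after study day 159 with a nominal Day 180 assessment but none at Day 210. For that patient, "Day 180 data will be carried forward to Day 210 for assessment of SRI-4 response".
- **Primary analysis, Table 2.** Item (2) restricts non-response by discontinuation by date: "Early withdrawals/discontinuations prior to study day 159 will be considered non-responders after the date of early withdrawal/discontinuation". Item (2)b then repeats the carry-forward for later stops without medication failure: "the Day 180 data will be carried forward to Day 210".
- **By-visit SRI-4.** Section 7.2.1 opens with "The primary analysis methods described in Section 7.1.1 and Table 2 will be repeated for each nominal visit". Further down it states "If a patient discontinues/withdraws early, the patient will be considered a non-responder after the date of discontinuation/withdrawal". Its only exception is a prior medication failure, which brings non-response forward to the failure date.
- **Endpoints that refer to 7.2.1.** SRI-5 (7.2.2), SRI-6 (7.2.3) and BICLA at Day 210 (7.2.7) cite both Section 7.1.1 with Table 2 and Section 7.2.1.
- **Continuous endpoints.** Approach 2 in Section 7.2.6.2 is labelled as corresponding to Sensitivity Analysis 2. Sensitivity Analysis 2 has "In case of early withdrawal/discontinuation after study day 159 but before Day 210 such that patient has Day 180 data"; Approach 2 has "In case of early withdrawal/discontinuation after Day 180 but before Day 210 such that patient has Day 180 data".

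**The concern.** Day 210 is both the primary time point and the last on-plan row of the by-visit SRI-4 analysis. The SAP gives two scores for the same patient at that visit. Someone who stops after study day 159, was a responder at the Day 180 assessment and has no Day 210 assessment is a responder under Table 2 and a non-responder under the 7.2.1 sentence.

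The report could then carry two Day 210 SRI-4 rates, both described as using primary methods. A reader setting the primary SRI-4 table beside the SRI-5, SRI-6 or BICLA tables at Day 210 could also be comparing different dropout rules. If the choice is left to programming, it may be settled late, when it should be fixed before unblinding.

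The Approach 2 mismatch is of the same kind. A patient stopping between study day 159 and Day 180 can be carried forward in Sensitivity Analysis 2 but excluded in the continuous analysis that claims to follow it.

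**Working it through.** **1. Can the two rules be read as one?**

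| Patient, no medication failure | 7.1.1 and Table 2, primary | 7.2.1 sentence |
|---|---|---|
| Stops before study day 159 | Non-responder after the stop | Non-responder after the stop |
| Stops on or after day 159, Day 180 present, Day 210 missing | Day 180 carried to Day 210 | Non-responder at Day 210 |

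The word early does not supply the missing limit, because 7.1.1 uses it for stops on or after day 159 and even for a stop on Day 210. Nor are the rules interchangeable elsewhere in the SAP. Scoring every stop before Day 210 as non-response is the discontinuation rule of Sensitivity Analysis 1, which uses no carry-forward and is listed as a separate analysis. Section 7.2.1 therefore conflicts with its own opening sentence in the second row of this table.

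**2. The plan's own sample size, to fix the denominators.** Section 3.3 gives 96 evaluable patients, 2:1, 62% against 33%, two-sided 10%, 80% power. With k = 2 and pooled rate (0.33 + 2 × 0.62)/3 = 0.5233:

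- Uncorrected placebo n = [1.645 × √(1.5 × 0.5233 × 0.4767) + 0.842 × √(0.33 × 0.67 + 0.62 × 0.38/2)]² / 0.29² = 26.6, so 27 + 54 = 81.
- Continuity-corrected n = (26.6/4) × [1 + √(1 + 2(k + 1)/(k × 26.6 × 0.29))]² = 31.6, so 32 + 64 = 96.

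The 96 is reproduced with the continuity correction. The denominators are 64 active and 32 placebo. Nothing in this point depends on which formula was used.

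**3. Size per patient.** One reclassified responder moves the Day 210 rate by 1/64 = 1.6 points (active) or 1/32 = 3.1 points (placebo).

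**4. Illustrative range.** The SAP does not say how many patients stop this late, so the counts below are assumptions. The start is the whole-patient count nearest the design rates: 40/64 (62.5%) and 11/32 (34.4%). The test is the uncorrected Pearson chi-square, with z = (p₁ − p₂)/√[p̄(1 − p̄)(1/64 + 1/32)]. For the start, p̄ = 51/96 = 0.531 and z = 0.281/0.108 = 2.60, giving p = 0.0092.

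| Late-stopping Day 180 responders, active + placebo | Rates under the 7.2.1 sentence | Difference (points) | p |
|---|---|---|---|
| 0 + 0 (equals primary) | 62.5% vs 34.4% | 28.1 | 0.0092 |
| 2 + 1 | 59.4% vs 31.2% | 28.1 | 0.0094 |
| 4 + 2 | 56.2% vs 28.1% | 28.1 | 0.0092 |
| 4 + 0 | 56.2% vs 34.4% | 21.9 | 0.043 |
| 6 + 0 | 53.1% vs 34.4% | 18.8 | 0.083 |
| 0 + 2 | 62.5% vs 28.1% | 34.4 | 0.0015 |

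Losses in proportion to arm size lower both rates and leave the difference and p almost unchanged. One-sided losses move both, in either direction.

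**5. Approach 2.** For a stop after study day 159 but not after Day 180, with an assessment that counts as Day 180 and none at Day 210, Sensitivity Analysis 2 carries Day 180 forward. Approach 2 lets its carry-forward exception start only after Day 180, so its general exclusion after withdrawal applies.

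**The case against.** The strongest reply is that 7.2.1 imports Table 2 in its first sentence, so the later sentence is only a summary and item (2)b governs. That is a possible reading, and it limits the claim. A reader might infer that the report is certain to show two Day 210 rates, and the SAP does not support that. Divergence needs literal programming and at least one patient who stops in the window, has Day 180 but no Day 210 data, is not a medication failure and responded at Day 180. Dosing ends at Day 180, so the group is narrow. The reply does not remove the contradiction, since the specific sentence departs from what it claims to repeat.

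Four other stronger inferences also fail.

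- **That the step from SRI-4 to SRI-5 and SRI-6 reflects a changed dropout rule.** The by-visit SRI-4, SRI-5 and SRI-6 analyses share the 7.2.1 wording. A mismatch arises only when the primary SRI-4 table is set against the secondary tables.
- **That the conflict readily flips significance.** Starting from 36/64 against 12/32 (p = 0.083), one active-only loss gives p = 0.112. That start is borderline, is not the design case and places the loss in one arm. From design-like counts, even six active-only losses stay below 0.10.
- **That the trial's conclusion is at risk.** Superiority is judged on the primary analysis, and 7.1.1 and Table 2 agree on the carry-forward for this group.
- **That Approach 1 needs the same correction.** It already carries the last data on or before withdrawal to all later assessments, whatever the day.

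On Approach 2 it can be said that Day 180 means the nominal visit, which Section 7.1.1 accepts from 159 days after first dose. That narrows the gap but does not close it: a stop on or before that visit is still treated differently, and the wording still differs from the analysis it claims to match.

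**Conclusion.** The contradiction stands as a matter of text. Section 7.2.1 states a discontinuation rule that, taken literally, gives a Day 210 by-visit result inconsistent with the primary analysis it says it repeats, and SRI-5, SRI-6 and BICLA at Day 210 inherit the ambiguity. Whether the two rates actually differ depends on how the sentence is programmed and on whether any eligible late-stopping responder exists; with none, they agree.

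The size is 1.6 points per active patient and 3.1 points per placebo patient, assuming 64 and 32 evaluable. From design-like counts, balanced losses leave p at about 0.009, and four or six active-only losses give 0.043 or 0.083. These counts are illustrations, because the SAP gives no number of late stops. The effect is confined to secondary displays and the primary test does not change. The Approach 2 cut-off is a separate, smaller inconsistency.

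Patients lacking both Day 180 and Day 210 data are a different question and are not covered here.

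**What to change.** - **Section 7.2.1.** Limit the non-responder sentence to discontinuation before study day 159, and state that later stops are scored by Table 2 item (2)b. The Day 210 row then equals the primary analysis, and SRI-5, SRI-6 and BICLA follow through their existing references.
- **Section 7.2.6.2, Approach 2.** Replace the Day 180 cut-off with study day 159, as in Sensitivity Analysis 2. Approach 1 needs no change.

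The cost is SAP wording, with programming checked against it before unblinding. No data collection, sample size or primary analysis changes.
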